8.2. Serious adverse events

A serious adverse event is an unexpected occurrence that (1) results in death, (2) is life-threatening, (3) requires hospitalization or prolongation of existing hospitalization or (4) results in persistent or significant disability or incapacity.

Given this research project consists of blood sample and collection of cells originating from the olfactory epithelium through non-invasive nasal brushing, we do not expect any prolonged or serious adverse event.

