8. SAFETY

8.1. Adverse event

An adverse event is defined here as a harmful and unintended occurrence in a subject participating to the study. All adverse events will be reported from the time a signed and dated informed consent form is obtained, until completion of the last study-related procedure.

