8.3. Potential adverse events

The blood sample may be perceived as slightly painful by the patient (however this feeling is temporary) and may result in a cutaneous hematoma.

The nasal brushing of the olfactory cleft may be perceived as uncomfortable or slightly painful by the patient. However, this feeling is temporary. No adverse effect has been reported in the literature.

Similarly to naso-pharyngeal swabs, it is possible that a slight bleeding occurs in some subjects with weakened mucosa. The risk of severe bleeding is extremely rare. A recent retrospective study investigating the risk of nasopharyngeal swabs found a rate of 8 complications (4 bleeding / 4 foreign body) out of a total of 643.284 patients (Koskinen et al. 2021). These complications were related to incorrect swabbing technique. Moreover, 1 study report CSF leak after naso-pharyngeal swab, occurring in a patient with meningoencephalocele (Sullivan et al. 2020). Because of the rarity of such skull base malformation and the fact that a nasal endoscopy will systematically be performed, we can assume that the risk of CSF leak is negligeable. Importantly, brushing will be performed by trained ENT specialists, ensuring a as atraumatic as possible brushing; and patients will be screened for factors that may predispose to severe bleeding. Moreover, if a bleeding occurs, adequate medical intervention will be ensured.

Additionally, one study demonstrated the safety of biopsy of olfactory neuroepithelium for the olfactory function (Andrews et al. 2016). Therefore, we can assume that the risk of olfactory dysfunction following a poorly invasive nasal brushing of the olfactory cleft is extremely low, especially since the procedure will be performed unilaterally. However, in the very unlikely event that a subject complains of olfactory dysfunction, specific medical measures will be taken.

Importantly, to avoid the discomfort due to blood sample and nasal brushing in pediatric population, these samplings will be performed during a general anesthesia that is planned for the routine medical management of these participants (eg. telomeropathy patients: marrow puncture; pediatric controls: tonsillectomy).

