8.5. Serious adverse event reporting procedures

A serious adverse event occurring to a research participant will be reported to the Ethics Committee that gave a favorable opinion of the study. Reports of related and unexpected serious adverse events will be submitted within 15 days after becoming aware of the event.

All serious adverse events that have not resolved by the end of the study, or that have not resolved upon discontinuation of the subject's participation in the study will be followed until any of the following occurs: (1) the event resolves, (2) the event stabilizes, (3) the event returns to baseline, if a baseline value is available, (4) the event can be attributed to agents other than the experiment, (5) when it becomes unlikely that any additional information can be obtained (subject or healthcare practitioner refusal to provide additional information, lost to follow-up after demonstration of due diligence with follow-up efforts).

Any event requiring hospitalization that occurs during the course of a subject's participation in a clinical study will be reported as a serious adverse event except hospitalizations for (1) social reasons in absence of an adverse event, (2) surgery or procedures planned before entry into the study, (3) clinic protocol procedures.

All of the medical investigators of this project are medical practitioners registered to l'Ordre des Médecins/Orde der Artsen. It will be left to their judgment to decide whether or not an adverse event is of sufficient severity to require the subject's removal from the study. A subject may also voluntarily withdraw from the study due to what he or she perceives as an intolerable adverse event.

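### The serious-event definition in 8.2 has no criterion for medically important events, so a brushing bleed that intervention keeps from becoming worse has no stated route to the ethics committee

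*Combined protocol and SAP*

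**What the plan says.** Section 8.2: "A serious adverse event is an unexpected occurrence that (1) results in death, (2) is life-threatening, (3) requires hospitalization or prolongation of existing hospitalization". The list closes with "4) results in persistent or significant disability or incapacity". No further item covers an event that is medically important, or that needed treatment to prevent one of the listed outcomes.

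Section 8.5 sets the route: "A serious adverse event occurring to a research participant will be reported to the Ethics Committee that gave a favorable opinion of the study". On timing it adds: "Reports of related and unexpected serious adverse events will be submitted within 15 days after becoming aware of the event". It also says that any event requiring hospitalization "will be reported as a serious adverse event except hospitalizations for" three listed reasons.

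For other events, 8.4 has the investigator record each one with its severity, relatedness and action taken. Section 8.1 says: "All adverse events will be reported from the time a signed and dated informed consent form is obtained". It names no recipient.

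Section 8.3 expects slight bleeding in some participants, calls severe bleeding extremely rare, and states: "Moreover, if a bleeding occurs, adequate medical intervention will be ensured".

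**The concern.** The protocol foresees a complication that will be treated, but its test of seriousness ignores treatment. It looks only at whether a bad outcome, a life threat or a hospital stay occurred. A bleed that was heading for one of these and was stopped by prompt intervention counts the same as no serious event.

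The setting makes this plausible. ENT specialists do the brushing (3.2), so treatment is at hand. Paediatric sampling is planned under a general anaesthesia arranged for other care (8.3), so a bleed controlled at that time need not cause an admission or a longer stay. Recruitment includes people with medullar aplasia, myelodysplasia and cirrhosis (section 4), and healthy adults and children are brushed as controls.

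Two things are at stake. The ethics committee, the only outside body the protocol names to receive event reports, could see none of these events while recruitment continues. And the study could report no serious adverse events for a technique that Endpoint #1 hopes will become a non-invasive clinical tool, although some complications had needed active treatment.

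**Working it through.** This is mainly a check of the text. Applying 8.2 and 8.5 to four kinds of bleed gives:

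| Bleed after brushing | Criterion met in 8.2 | Route to the committee |
|---|---|---|
| Life-threatening, wherever treated | second | yes, under 8.5 |
| Leads to admission or prolongs a stay | third | yes, under 8.5 |
| Stopped by intervention before any listed outcome | none | none stated |
| Slight and self-limiting | none | none stated, and none needed |

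The third row is the gap. Such an event is recorded (8.4) and reported to an unnamed recipient (8.1).

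The first two rows depend on the word *unexpected*. Section 8.2 builds it into the definition of seriousness, while 8.5 uses it, with relatedness, as a further filter on events that are already serious. Because 8.3 foresees bleeding, a reader could argue that even a grave bleed is expected and so falls outside 8.2. The hospitalization sentence in 8.5 carries no such condition, so the two sections conflict for a foreseen bleed that leads to admission. Under 8.5 the 15-day limit attaches only to related and unexpected serious events, so a foreseen serious bleed would have no deadline.

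**How many events?** The plan states no expected number. The number without a route is N × p × (1 − a), where N is the number brushed, p is the probability of a bleed needing intervention, and a is the share of those meeting one of the four criteria.

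- N: 150 patients and 100 controls (2.2).
- p, low end: 8.3 cites 4 bleeding complications in 643,284 patients having nasopharyngeal swabs, so p = 4 / 643,284 ≈ 6 per million. This is a different procedure in a different population.
- p, higher values: 1% and 5%. These are assumptions; the documents give no rate for olfactory-cleft brushing in these patients.
- a: not given in the documents, so left open.

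Expected bleeds needing intervention, N × p:

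- Swab figure: 150 × 4 / 643,284 ≈ 0.001 in patients; 250 × 4 / 643,284 ≈ 0.002 in all participants.
- 1%: 150 × 0.01 = 1.5 in patients; 250 × 0.01 = 2.5 in all.
- 5%: 150 × 0.05 = 7.5 in patients; 250 × 0.05 = 12.5 in all.

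The number without a route lies between zero (a = 1) and these values (a = 0).

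**The case against.** The strongest reply is that little escapes. A life-threatening bleed meets the second criterion wherever it is treated. Any event that leads to admission meets the third, and so does one that delays a child's discharge, because prolongation of a stay is listed. Every other event is recorded with severity, relatedness and action taken, and section 10 opens the records to monitors, auditors and inspectors. The protocol also has safeguards: endoscopic screening, exclusion for abnormal endoscopic findings, trained operators, and a promise to screen for factors predisposing to severe bleeding. At the swab rate the committee would expect essentially no report under any definition. Nothing in the documents makes a fifth criterion obligatory.

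Most of this stands, and it limits the point. A reader might infer that any bleed or CSF leak treated on the spot never reaches the committee. The text does not support that: on-site treatment does not remove an event from the second or third criterion, and 8.1 and 8.4 leave onward reporting unstated rather than barred. Nor does the text support using CSF leak as the main example. Section 8.3 judges that risk negligible, and nothing suggests a leak would be managed without admission.

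The reply does not close the third row of the table. A record open to inspection is not a report to the committee. The swab figure does not settle the rate either, since the site brushed and the population both differ.

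**Conclusion.** The point holds in a narrow form. A brushing complication, chiefly a bleed, that needs intervention to prevent a listed outcome but meets none of the four criteria has no stated route to the ethics committee. This follows from 8.2 and 8.5 alone and needs no assumed rate.

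Its size is uncertain: between about 0.001 and 7.5 expected treated bleeds among the 150 patients, the upper value resting on an assumed 5%. The documents do not say how many of these would meet a criterion. A reader might want to state the share that would go unreported, but any such figure only restates whatever admission share is assumed, so none is given here.

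This is a cheap improvement to safety reporting. It does not affect the analysis of any endpoint, and it is not evidence that harm would be concealed.

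**What to change.** 1. In 8.2, add a fifth criterion: *or is medically important in the investigator's judgement, that is, needs medical or surgical intervention to prevent one of the outcomes above*.
2. Remove *unexpected* from the 8.2 definition, or reconcile it with 8.5, so that a complication foreseen in 8.3 is not excluded. Without this step the new criterion could be argued away for the very event it is meant to catch.
3. In 8.5, state that brushing-related events meeting the new criterion go to the ethics committee within the 15-day limit already there, whether or not the participant is admitted. State also that minor self-limiting or trivially treated nosebleeds remain non-serious, so that not every treated nosebleed becomes a serious event.
4. In 8.1 and 8.4, name who receives reports of non-serious events.

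The cost is a few sentences and possibly a few more reports to the committee. The count of serious events may look slightly less favourable. No visit, procedure or treatment changes.

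A neighbouring gap deserves attention in the same edit: under 8.1 adverse events are collected "until completion of the last study-related procedure", so a bleed that starts later may fall outside collection altogether. The steps above do not close it.

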8.3. Potential adverse events

The blood sample may be perceived as slightly painful by the patient (however this feeling is temporary) and may result in a cutaneous hematoma.

The nasal brushing of the olfactory cleft may be perceived as uncomfortable or slightly painful by the patient. However, this feeling is temporary. No adverse effect has been reported in the literature.

Similarly to naso-pharyngeal swabs, it is possible that a slight bleeding occurs in some subjects with weakened mucosa. The risk of severe bleeding is extremely rare. A recent retrospective study investigating the risk of nasopharyngeal swabs found a rate of 8 complications (4 bleeding / 4 foreign body) out of a total of 643.284 patients (Koskinen et al. 2021). These complications were related to incorrect swabbing technique. Moreover, 1 study report CSF leak after naso-pharyngeal swab, occurring in a patient with meningoencephalocele (Sullivan et al. 2020). Because of the rarity of such skull base malformation and the fact that a nasal endoscopy will systematically be performed, we can assume that the risk of CSF leak is negligeable. Importantly, brushing will be performed by trained ENT specialists, ensuring a as atraumatic as possible brushing; and patients will be screened for factors that may predispose to severe bleeding. Moreover, if a bleeding occurs, adequate medical intervention will be ensured.

Additionally, one study demonstrated the safety of biopsy of olfactory neuroepithelium for the olfactory function (Andrews et al. 2016). Therefore, we can assume that the risk of olfactory dysfunction following a poorly invasive nasal brushing of the olfactory cleft is extremely low, especially since the procedure will be performed unilaterally. However, in the very unlikely event that a subject complains of olfactory dysfunction, specific medical measures will be taken.

Importantly, to avoid the discomfort due to blood sample and nasal brushing in pediatric population, these samplings will be performed during a general anesthesia that is planned for the routine medical management of these participants (eg. telomeropathy patients: marrow puncture; pediatric controls: tonsillectomy).

8.4. Reporting procedures for all adverse events

All adverse events occurring during the study observed by the investigator or reported by the subject, whether or not attributed to the study, will be recorded. The following information will be assigned by the investigator: description, date of onset and resolution, severity, assessment of relatedness to the experiment, and action taken. The investigator may be asked to provide follow-up information. All related adverse events that result in a subject's withdrawal from the experiment will be followed up until a satisfactorily resolution occurs.

8.5. Serious adverse event reporting procedures

A serious adverse event occurring to a research participant will be reported to the Ethics Committee that gave a favorable opinion of the study. Reports of related and unexpected serious adverse events will be submitted within 15 days after becoming aware of the event.

All serious adverse events that have not resolved by the end of the study, or that have not resolved upon discontinuation of the subject's participation in the study will be followed until any of the following occurs: (1) the event resolves, (2) the event stabilizes, (3) the event returns to baseline, if a baseline value is available, (4) the event can be attributed to agents other than the experiment, (5) when it becomes unlikely that any additional information can be obtained (subject or healthcare practitioner refusal to provide additional information, lost to follow-up after demonstration of due diligence with follow-up efforts).

Any event requiring hospitalization that occurs during the course of a subject's participation in a clinical study will be reported as a serious adverse event except hospitalizations for (1) social reasons in absence of an adverse event, (2) surgery or procedures planned before entry into the study, (3) clinic protocol procedures.

All of the medical investigators of this project are medical practitioners registered to l'Ordre des Médecins/Orde der Artsen. It will be left to their judgment to decide whether or not an adverse event is of sufficient severity to require the subject's removal from the study. A subject may also voluntarily withdraw from the study due to what he or she perceives as an intolerable adverse event.

9. DATA ANALYSIS

Blood samples collected at CUSL will be analyzed at the laboratory of the Cliniques universitaires Saint-Luc, where leukocyte telomere length will be analyzed using a validated Flow-FISH technique (Prof. [name], head of biologogical hematology department), developed by Prof [name] (UCLouvain).

Cellular material harvested through the nasal brushing will be processed at the laboratory of Prof. [name] (UCLouvain) and at the laboratory of Genetics of CUSL (Prof. [name]).

10. DIRECT ACCESS TO SOURCE DATA/DOCUMENTS

The investigator will allow trial-related monitoring, audits, and regulatory inspections, and provide direct access to source data and documents to authorized auditors and monitors.

11. ETHICS

11.1. Declaration of Helsinki

The investigator will ensure that the study is conducted in full conformity with the current revision of the Declaration of Helsinki (last amended October 2000, with additional footnotes added in 2002 and 2004).

11.2. Informed consent

A written version of informed consent form will be presented to the subject and /or her/his parents detailing: the exact nature of the experiment, the implications and constraints of the protocol, the known side effects, and any risks involved in taking part. It will be clearly stated that the subject is free to withdraw from the study at any time for any reason without prejudice to future care, and with no obligation to give the reason for withdrawal.

The subject and/or her/his parents will be allowed as much time as wished to consider the information, and the opportunity to question any or all investigators listed in the ethics application, their general practitioner or other independent parties to decide whether they will participate in the study.

Written Informed Consent will then be obtained by means of subject's dated signature and/or parent's dated signature, signature of the person who presented the informed consent and, if different, the principal investigator.

A copy of the signed Informed Consent will be given to the subject. The original signed form will be retained at the study site.

11.3. Independent ethics committee

A copy of the protocol, the informed consent form, subject information sheet, and any proposed advertising material will be submitted to an Independent Ethics Committee for approval.

The principal investigator will submit and, when necessary, obtain approval from the Committee for all subsequent protocol amendments and changes to the informed consent document.

The investigator will notify substantial amendments to the protocol and will notify the Committee of these in accordance with local procedures.

11.4. Subject confidentiality

The investigator will ensure that the subject's anonymity is maintained. The subject will be identified by a subject ID number. As described in section 14, all documents will be stored securely and kept in strict confidence.

12. DATA HANDLING AND RECORD KEEPING

All the data will be pseudonymized thanks to the use of a specific identification code. The subject will be identified through this identification code, which will depend on the study, on the group of subjects and on the inclusion order. Pseudonymized data will be recorded in a protected RedCap database.

Data protection will be ensured by the law of the July 30, 2018 relating to the protection of privacy and by Belgian and European regulations (European General regulation on the protection of personal data (GRPD) of May 25, 2018). These rights will also be guaranteed by the law of April 22, 2002 relating to the rights of the patients.

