2.2 STUDY DESIGN

This study is a monocentric prospective interventional study on 250 subjects (150 patients and 100 controls). The promotor of this study is the Cliniques universitaires Saint-Luc (Brussels, Belgium).

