2.2.2 Study endpoints

Endpoint #1: To assess the suitability of nasal brushing analyses and blood tests for the diagnosis of telomeropathies.

Rationale

To date, the complete diagnosis of telomeropathies, including the identification of responsible mutations, is based on blood samples and fibroblast cultures obtained through skin biopsies. Cells obtained through nasal brushing offer the opportunity to detect mutations involved in telomeropathies, in a mildly invasive way. We will thus assess a population of patients with a suspicion of telomeropathy, using a combination of blood tests and nasal brushings, and will compare their nasal brushing results to those of age-matched healthy controls. If we confirm that the nasal brushing offers the opportunity to i) detect damaged telomeres and premature cellular senescence and ii) identify mutations related to telomeropathies, this technique could become a non-invasive clinical tool for the diagnosis work-up of telomeropathies

Assessments

We will collect blood samples in each patient and will perform a nasal brushing to each subject (patients and controls) included in this study. One sample of blood will be collected for each patient and processed following the protocol further described (see chapter 3.1.).

For nasal brushing, one collection will be performed in the most accessible nostril. We will evaluate if it is possible to detect damaged telomeres and premature cellular senescence in patient, in comparison to healthy controls.

In the patients group, collected cells will be split into three parts, two will be devoted to Endpoint#1, and the other for the Endpoint #2, following the protocol further described (see chapter 3.2.).

For patients recruited from the pediatric consultation, if possible, this sample will be collected during another medical procedure planned under general anesthesia (eg. marrow puncture). Similarly, pediatric controls will be recruited among patients undergoing elective otorhinolaryngological surgery (eg. grommets, tonsillectomy).

Endpoint #2: To develop primary cell cultures for the functional study of new germline mutations.

Rationale

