3.2. NASAL BRUSHINGS

The nasal brushings will be performed by Prof. [name] or [name], trained ENT specialists, during their scientific time. For patients and controls recruited among patients from the clinic, nasal brushings will be performed while these subjects are at the clinic for their standard cares. For controls recruited outside the clinic, the nasal brushing will require a specific study consultation.

A local vasoconstrictor (Xylometazolin, 1mg/ml) will be applied at the level of the head of the inferior turbinate with the use of a nasal tampon to facilitate the visibility and the access to the olfactory cleft. Each nostril will be assessed, using a 30° rigid endoscope of 4mm (Karl Storz[®], Tuttlingen, Germany), in order to identify the nostril having the most accessible olfactory cleft. This nostril will be chosen to receive the brushing. A sterile disposable cytology brush (i.e. FLOQSwabs, Copan[®], Italy) will be gently rolled on the mucosal surface, at the level of the head of the middle turbinate, as described previously (Orrù et al., 2014). Two brushings will be done for each subject. The brush will then be immerged in a conical centrifuge tube containing DMEM-F12 medium supplemented with GlutaMAX. Cellular material will then be dissociated from the brush using disposable micropipette tips.

In the patients group, cellular material will be split into three parts for specific processing. A first part will be cultured (Prof [name]' lab, de Duve Institute) (Endpoint #2), a second one will be processed by Cytospin for future stainings (Endpoint #1) (Prof [name]' lab, de Duve Institute) and the last part will be kept frozen and further used for whole exome sequencing (Endpoint #1), if the suspicion of telomeropathy has been confirmed. This latter step will be performed at the laboratory of genetics of CUSL (Prof. [name]) In the control group, cellular material will be exclusively used for the staining evaluating the degree of senescence and damages to telomeres.

A Figure is enclosed to this document to summarize experimental procedures and samples flow.

Figure summarizing experimental procedures and samples flow in patients (A) and controls (B)

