13. FINANCING AND INSURANCE

The study will be funded by grants obtained by Prof. [name] and Prof. [name].

Blood sample analysis and genetic analysis (whole-exome sequencing) will only be performed in patients. For patients involved in the current study, Flow-Fish analysis is already performed in clinical routine as standard of care procedure. Similarly, genetic analysis on cellular material is considered as a standard of care for patients with suspicion of telomeropathy. Therefore, these analyses will not be associated to additional costs, neither in term of material of personal.

Indemnity for negligent and non-negligent harm will be provided by a specific insurance provided by the Cliniques universitaires Saint-Luc. Company:

Police number:

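### The only subject code described includes the group, and the text gives no group-free slide label or masked reading, so stain readers may know who is a patient

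*Combined protocol and SAP*

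**What the plan says.** Section 12 (Data handling and record keeping) pseudonymises all data with an identification code "which will depend on the study, on the group of subjects and on the inclusion order", and the data go into a database. Section 11.4 mentions a subject ID number but does not say how it is built.

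Under Endpoint #1, section 2.2.2 says the investigators "will compare their nasal brushing results to those of age-matched healthy controls". The features sought are damaged telomeres and premature cellular senescence.

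Section 3.2 treats the groups differently. For patients: "In the patients group, cellular material will be split into three parts for specific processing", that is, culture, Cytospin slides for staining, and frozen cells for exome sequencing. For controls: "In the control group, cellular material will be exclusively used for the staining evaluating the degree of senescence and damages to telomeres". The section also announces a "Figure summarizing experimental procedures and samples flow in patients (A) and controls (B)", which was not available for this review.

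Section 9 says "Cellular material harvested through the nasal brushing will be processed at the laboratory of" two named units and stops there. Section 13 adds: "Blood sample analysis and genetic analysis (whole-exome sequencing) will only be performed in patients".

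**The concern.** A patient-control comparison of microscopy stains is exposed to reader expectation when a person decides which cells count as senescent or which telomeres as damaged. Here the expected direction is fixed in advance, because the introduction describes telomere damage as a typical feature of patients' cells.

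A reader could learn the group in two ways. The slide could carry the section 12 code, which includes the group. Or the person who divides the cells could also read the slides, since only patient cells are divided.

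At stake is the claim that nasal brushing can separate patients from healthy controls, and hence that it could become a diagnostic tool. Blood and exome analyses are not done in study controls, so no other Endpoint #1 result from those controls could expose a biased stain comparison. The mutation and Flow-FISH results are not affected.

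**Working it through.** The main check is textual. The plan gives no test, alpha, SD or scoring method for the stains, so it has no figure of its own to reproduce.

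**1. Which identifiers are described?**

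| Section | Identifier | Structure given |
|---|---|---|
| 11.4 | Subject ID number | None |
| 12 | Identification code | Study, group, inclusion order |
| 3.2, 9 | Slide or sample label | None mentioned |

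The plan does not define the groups in section 12. Patient versus control is the natural reading, because section 3.2 uses the word in that sense.

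**2. Which Endpoint #1 readouts exist in both groups?**

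| Readout | Patients | Study controls |
|---|---|---|
| Flow-FISH on blood | Yes | No (section 13) |
| Exome sequencing | Yes, if suspicion is confirmed (section 3.2) | No (section 13) |
| Senescence and telomere-damage stains | Yes | Yes (section 3.2) |

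Only the stains allow a comparison with study controls. Olfactory testing is also done in both groups, but it belongs to Endpoint #3.

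**3. Is masked or automated reading stated?** Sections 2.2.2, 3.2 and 9 are where it would be expected. None of them, and no other part of the available text, mentions a recoding step, a masked reader or an automated scoring rule.

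**4. How large a reader shift would matter? (illustration only)**

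Inputs: "250 subjects (150 patients and 100 controls)" from section 2.2. Assumed: two-sided alpha 0.05, one continuous score expressed in SD units, and no true group difference. The two smaller cases, 75 v 50 (half the slides readable) and 40 v 25, are also assumptions.

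SE of the group difference = √(1/n₁ + 1/n₂). With an average reader shift b, the false-positive rate is P(|Z + b/SE| > 1.96).

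To reach 0.10, b/SE must be about 0.652:
- upper tail: P(Z > 1.96 − 0.652) = P(Z > 1.308) ≈ 0.0955
- lower tail: P(Z < −1.96 − 0.652) = P(Z < −2.612) ≈ 0.0045
- sum ≈ 0.100

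| Readable slides | SE (SD units) | Shift that doubles 5% to 10% |
|---|---|---|
| 150 v 100 | √(1/150 + 1/100) = 0.1291 | 0.084 SD |
| 75 v 50 | √(1/75 + 1/50) = 0.1826 | 0.119 SD |
| 40 v 25 | √(1/40 + 1/25) = 0.2550 | 0.166 SD |

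Read the other way, at 150 v 100 a shift of 0.1, 0.2, 0.3 or 0.5 SD gives a false-positive rate of about 0.12, 0.34, 0.64 or 0.97. Nothing in the documents says whether a shift of any of these sizes would occur.

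**The case against.** The strongest reply is that section 12 concerns the database. It says nothing of slides or tubes, and the step from code to slide is an inference. The harm is also conditional: a reader must learn the group, a person must make the judgement, and that knowledge must move the score. The documents settle none of these, and scoring may be automated. The figure that could not be seen might show a neutral label. The illustration has no counterpart in a plan that specifies no test. Finally, masking is only one part of a wider silence in section 9 about how the stains are scored and analysed.

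Most of this is right as far as it goes, and it limits the point: section 12 is not proof that readers will be unmasked, and no size of bias can be claimed. It does not remove the point. The text offers no other slide label, and the different handling of the two groups could reveal the group even if the section 12 code never reached a slide. A figure might settle the label, but the written plan would still lack a reading rule.

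It can also be said that masking to group alone leaves a reader free to learn a patient's Flow-FISH or exome result, and that slides from the two groups should be mixed in batches. Both are reasonable additions. Neither makes the basic fix unsound.

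**Conclusion.** The concern holds. Followed as written, the plan combines a code that includes the group, visibly different handling of the two groups, and no stated masking. That leaves the only patient-control comparison under Endpoint #1 open to reader bias. The plan should be changed on this point.

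Confidence is medium. The gap in the available text is clear, but laboratory practice is unknown. The conclusion assumes that a person makes at least part of the scoring judgement and that the unseen figure does not already provide for neutral labels and masked reading. The size of any bias cannot be given. The illustration shows only that, under its assumptions, an average shift of roughly 0.08 to 0.17 SD would be enough to double a 5% error rate. The case for the change does not rest on those figures.

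**What to change.** - **Section 12:** keep the present code for the database. Add that slides for staining carry a separate random number with no group information.
- **Section 3.2:** state that this number is assigned once slides are prepared, by existing study staff who do not score them, and that the key stays closed to readers until scoring is locked. Relabelling after preparation deals with both the code and the difference in handling.
- **Section 9:** state that readers of the senescence and telomere-damage stains are masked to group.
- **If the sample-flow figure already sets a neutral slide label:** refer to it in sections 3.2 and 12, and add only the masking sentence.
- **Optional:** mask readers to Flow-FISH and exome results as well, and mix patient and control slides within staining and reading batches.

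The core change needs wording in three sections and no new assay or visit. Its cost is one relabelling step per subject, up to 250, and a restricted key that someone outside the reading team must hold. It needs to be in place before slides are read, because a slide already scored with the group known cannot be made masked afterwards without a fresh reading.
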